Two DLTs were reported on the trial, both occurring in the 0.07 mg treatment group (increased knee pain and tachycardia paroxysmal [also an SAE as noted above]). The DLT of increased knee pain was considered probably related to treatment by the reporting investigator.

Single intra-articular injections of SM04690 at doses of 0.03 mg, 0.07 mg, and 0.23 mg in a 2 mL suspension into the target knee joint appeared to be safe and well-tolerated in subjects with moderately to severely symptomatic OA of the knee. No clinically significant safety concerns or differences between active and placebo treatment groups were noted with regard to AEs, clinical laboratory results, vital signs, ECGs, assessment of bone loss, assessment of bone marrow edema, or assessment of inflammatory cytokines.

An interim analysis of the phase 2 SM04690-OA-02 study was performed in October 2016 after all subjects completed their Week 26 visit. Summarizing the safety events occurring within these 26 weeks and summarized in the interim analysis, 8 SAEs have been reported in 7/452 (1.5%) subjects. The SAEs reported have been Hypertensive crisis, Cholecystitis acute, Gall bladder adenocarcinoma, Uterine prolapse, Diverticulitis, Patella fracture, Osteoarthritis (of the hip), and Non-cardiac chest pain. These events were felt to be either not related or unlikely related to study medication by investigator assessment.

Study Placebos

The 2 possible placebo injections in this study will be either 2 mL of vehicle, which is the inactive substance carboxymethylcellulose sodium and polysorbate 80, or a 0 mL sham injection. The inactive substance carboxymethylcellulose sodium and polysorbate 80 is often used as a food or drug additive. Potential risks associated with carboxymethylcellulose sodium and polysorbate 80 include allergic reaction and hypersensitivity.

The placebo sham injection contains no substance and has the same risks associated with the knee joint injection which include bleeding, bruising, infection, pain at the injection site, swelling of the knee, and/or injury to knee joint.

Risks of Injection

Risks associated with knee joint injection include bleeding, bruising, infection, pain at the injection site, swelling of the knee, and/or injury to knee joint.

Risks of Topical Anesthetics

Reactions to the topical anesthetic drug that may be applied to the subjects' skin are rare and may consist of cutaneous lesions (patches of skin that contrast with surrounding skin due to differences in texture, thickness, and color), or urticaria (red, raised itchy bumps). In addition to the local reactions, systemic reactions, although much rarer than the local ones, can be seen and include edema, bradycardia, dizziness, drowsiness, paresthesia, nausea, vomiting, or anaphylactoid reactions (generalized itching and hives, swelling, wheezing and difficulty breathing, fainting, and/or other allergy symptoms).

Blood Sampling

There is some risk of pain or local bruising and infection at the site where blood is drawn for laboratory tests. There is also a small risk of a fainting episode, which can occur as a reaction to donating blood.

Knee Radiograph

This study involves radiation exposure from a total of 2 radiographs of the subjects' knees on 2 different days, each approximately 6 months apart. As part of everyday living, everyone is exposed to a small amount of background radiation that comes from soil, rocks, outer space, and within the body itself. The radiation dose for all knee X-rays that the subject will receive in this study is expected to be approximately 0.01 mSv and is less than 1 days' equivalent dose from background radiation. The risk from this dose is small. This radiation exposure may not be necessary for the subjects' medical care, but it is necessary to obtain the research information desired.

2.3.2 KNOWN POTENTIAL BENEFITS

Taking part in this study may or may not provide any benefit to the subject. Information from this study may help doctors learn more about treatments for OA and this information may help future subjects, even if it may not help the subjects in this study.

3. OBJECTIVES AND PURPOSE

The purpose of this study is to evaluate the safety and efficacy of SM04690 injected in the target knee joint of moderately to severely symptomatic OA subjects.

Primary objective:

The primary objective of this study is to determine the effective dose(s) of SM04690 for the treatment of knee OA.

Secondary objective:

The secondary objective of this study is to evaluate the safety and tolerability of SM04690.

4. STUDY DESIGN AND ENDPOINTS

4.1 DESCRIPTION OF THE STUDY DESIGN

This study is a multicenter, randomized, double-blind, placebo-controlled, parallel group study of four different concentrations of SM04690 injected into the target knee joint of moderately to severely symptomatic OA subjects.

Approximately 630 subjects will be consented and randomized using a permuted block design to 6 treatment arms (0.03 mg active per 2 mL injection : 0.07 mg active per 2 mL injection : 0.15 mg active per 2 mL injection : 0.23 mg active per 2 mL injection : 0.0 mL vehicle : 2.0 mL vehicle). To support the primary objective, active treatment groups will be compared to both vehicle (2.0 mL vehicle) and sham (0.0 mL vehicle). Subjects will participate in a screening period of a minimum of 10 days and up to 22 days and a 24-week follow-up period. Clinic visits will be scheduled at Screening Visit 1, Screening Visit 2, Day 1, and Weeks 4, 12, and 24 (EOS)/ET. Specific timing of protocol procedures is described in the Schedule of Events Table (Section 7.3.6). Specific timing of electronic diary and questionnaire completion is described in the Schedule of Electronic Diary and Questionnaire Completion Table (Section 7.3.7).

This study will be conducted at approximately 80 investigational centers in the US.

In this study, subjects will be required to complete an electronic diary for the following:

- Daily pain NRS
- Daily monitoring of usage of NSAIDs
- Weekly completion of the KOOS-PS
- Monthly completion of the WOMAC
- Monthly completion of KOOS
- Monthly completion of Patient Global Assessment

A Widespread Pain Index and Symptom Severity (WPI&SS) assessment will be administered at Screening Visit 1. Physician Global Assessment will be performed at Day 1 and Weeks 4, 12, and 24 (EOS)/ET. Evaluation of the success of blinding will be performed at Day 1 (post intra-articular injection) and Week 24 (EOS)/ET.

In addition, general medical evaluations including physical examination, knee examination, and recording of vital signs will be performed at Screening Visit 1, Day 1, and Weeks 4, 12, and 24 (EOS)/ET. Height will be measured at Screening Visit 1 and weight will be measured at Screening Visit 1 and Week 24 (EOS)/ET. Clinical laboratory evaluations will be performed at Screening Visit 1 and Weeks 4, 12, and 24 (EOS)/ET. Radiographic imaging of the knees will be performed at Screening Visit 1 and Week 24 (EOS)/ET.

Recording of signs and symptoms of study medication intolerability and TEAE reporting will start following the injection of the study medication and continue until the subject completes Week 24 (EOS)/ET. All TEAEs, whether volunteered, elicited, or noted during examination, will be recorded throughout the study.

Subject Re-Screening

Subjects are allowed to be re-screened once. Re-screens are limited to subjects who did not meet inclusion/exclusion criteria due to a transient reason. Transient refers to self-limiting and predictably resolving conditions or acute events (e.g., common cold, or otitis media), reversible medical conditions that are successfully treated (e.g., anemia successfully treated by infusion), and/or being unable to comply with study procedures due to administrative convenience (e.g., family issues or attending to a private matter). Diary non-compliance is not a transient event and subjects with diary non-compliance may not be re-screened.

Subjects who failed any entry criteria for which no further treatment or spontaneous resolution is expected are not allowed to be re-screened.

Any re-screened subject must be re-consented and will be issued a new subject number. All screening procedures and assessments, except for the knee radiograph (if taken at previous screen), must be performed at re-screen; no results or data, except for the knee radiograph, may be used from the previous screen. Target knee selection may not be changed at re-screen.

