7.3 STUDY SCHEDULE

7.3.1 SCREENING

Screening Visit 1

The Investigator or designee must explain the nature of the study protocol and associated risks to the potential study participant. The potential participant must be allowed to review the study information and to ask questions before being asked to sign the informed consent form. Written informed consent must be provided by the potential study participant prior to initiation of any screening evaluations or other study-related procedures. The signature, date, and the name of the individual at the site who obtained the informed consent will be recorded in the subject's source record. After written informed consent is obtained, the subject will be assigned a subject number.

The following procedures and assessments will be performed 10-22 days prior to Day 1:

- Documentation of demographic information, including date of birth, gender, race, and ethnicity
- Documentation of current and past medical history including assistive device usage, documentation of current medications, and review of prior medication excluded by the protocol
- Physical examination, including knee examination of both knees and selection of target knee
- Vital signs measurements (pulse, blood pressure, respiration rate, and temperature)
- Height and weight measurements
- Venipuncture and collection of samples for clinical laboratory tests
- Pregnancy test (serum-based)
- Urine drug test
- WPI&SS assessment
- Radiograph – bilateral in weight-bearing fixed flexion position, posterior-anterior (PA) view X-ray

Results from these evaluations will be compared with inclusion/exclusion criteria to determine subject eligibility. In order to complete randomization, WPI&SS scores and subject bilateral/unilateral OA of the knee status from Screening Visit 1 must be entered into EDC prior to the study reaching the enrollment caps described in [Section 7.3.2](#).

Investigators will maintain a confidential log of all subjects who have been screened for participation in the study whether or not the subject was eligible for study participation.

Screening Visit 2

This visit must occur at least 3 days after Screening Visit 1 and between 7 to 12 days (inclusive) prior to Day 1.

This visit should occur after confirmation of eligible pregnancy test (if applicable), radiograph, clinical laboratory, and urine drug test report results.

The following procedures and assessments will be performed at Screening Visit 2:

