7.3.4 FINAL STUDY VISIT

Week 24 End of Study (EOS)

This final study visit should occur on Day 169 with a window of + 7 days.

The following procedures and assessments will be performed at Week 24 (EOS):

- Collection of TEAE and concomitant procedures/therapies/medication data
- Review of medical history
- Vital signs measurements (pulse, blood pressure, respiration rate, and temperature)
- Physical examination, including knee examination of both knees
- Weight measurement
- Venipuncture and collection of samples for clinical laboratory tests
- Radiograph – bilateral in weight-bearing fixed flexion position, posterior-anterior (PA) view X-ray
- Physician Global Assessment
- Evaluation of success of blinding
- Return of electronic device

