9. STATISTICAL CONSIDERATIONS

9.1. Baseline

Baseline is defined as the last value recorded for any given parameter prior to study medication injection. If a subject never received a study injection, baseline is defined as the last value recorded prior to study termination.

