9.2. Early Termination

If a subject discontinues the study, early termination assessments will be performed according to the protocol. If these assessments occur within the window of a scheduled visit (+3 days for Weeks 4 and 12 and +7 days for Week 24), they will be associated with that visit for the purposes of FAS and mFAS analysis.

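### SAP 9.2's one-sided window drops ET knee films taken shortly before Day 169 from mJSW, and a baseline film reused at re-screening has no age limit

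*Protocol*

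**What the plan says.** **Timing of the two films.** The Screening Visit 1 list in Protocol 7.3.1, which includes the radiograph, opens: "The following procedures and assessments will be performed 10-22 days prior to Day 1". For Week 24, Protocol 7.3.4 says: "This final study visit should occur on Day 169 with a window of + 7 days". Protocol 2.3.1 describes radiographs of the subjects' "knees on 2 different days, each approximately 6 months apart". SAP 5.2.9 names no other film.

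**Early termination.** Protocol 7.3.5 includes a radiograph among the ET procedures, to be done if possible within 14 days of withdrawal. SAP 9.2 links ET assessments to a scheduled visit for the FAS and mFAS if they fall inside that visit's window, given as +"3 days for Weeks 4 and 12 and +7 days for Week 24), they will be associated with that visit". No days before the nominal visit day are allowed.

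**Missing data.** SAP 9.4 imputes nothing in the main efficacy analyses. Its LOCF and MMRM sensitivity analyses cover pain NRS, WOMAC Pain, WOMAC Function and PTGA. The MMRM list in SAP 7.5.2 also omits mJSW.

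**Re-screening.** Protocol 4.1: "Subjects are allowed to be re-screened once". It continues: "All screening procedures and assessments, except for the knee radiograph (if taken at previous screen), must be performed at re-screen", and adds that "no results or data, except for the knee radiograph, may be used from the previous screen". Neither a maximum film age nor a maximum gap between screens is stated. SAP 9.1: "Baseline is defined as the last value recorded for any given parameter prior to study medication injection". That definition has no age limit either.

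**The concern.** The +7 days in Protocol 7.3.4 is a scheduling tolerance: a subject who stays in the study should come on or just after Day 169. SAP 9.2 turns it into an analysis window for subjects who leave early, and most of those are seen before Day 169. A film taken one day short is then unusable for mJSW. No earlier post-baseline film exists to carry forward or to model, so the subject contributes nothing to this primary endpoint. It is also the only one of the four primary endpoints without a missing-data sensitivity analysis.

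The reused film is a separate matter. For a re-screened subject, the measured change can include a stretch of pre-injection change that the analysis labels as part of a 24-week change. The protocol guards against stale baselines elsewhere: Protocol 7.3.2 screen-fails a subject with more than 12 days between Screening Visit 2 and Day 1, because the baseline questionnaires would be too old. The radiograph has no matching rule once it is carried over.

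**Working it through.** **Inputs.** Baseline film 10 to 22 days before Day 1 (Protocol 7.3.1). Week 24 film on Days 169 to 176, that is 168 to 175 days after Day 1 (7.3.4). ET procedures within 14 days of discontinuation (5.5.2). Diary week *k* is Day 7*k* - 6 to Day 7*k* (SAP 9.3). Week 24 WOMAC on Day 167 or 168 (Protocol 7.3.7). First consent April 2017 and last completion March 2018, both estimates (Protocol Summary). About 630 subjects in six equal arms (10.5). The documents give no discontinuation rate, re-screen rate, narrowing rate or SD of mJSW change.

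**1. Planned film interval, no reuse.** Shortest: 168 + 10 = 178 days. Longest: 168 + 7 + 22 = 197 days. At 30.44 days per month this is 5.8 to 6.5 months, which reproduces the protocol's figure of about 6 months.

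**2. An ET visit on Day 168.**
- mJSW: Day 168 lies outside Days 169 to 176, so the film is not assigned to Week 24 and the value is missing.
- Pain NRS: Week 24 is Day 7 × 24 - 6 = 162 to Day 168. Entries on Days 162 to 167 give six of seven, and SAP 5.2.1 needs four.
- WOMAC: an entry on Day 167 is on schedule.

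The 14-day allowance makes the result depend on the appointment. A subject who leaves on Day 160 may be filmed up to Day 174. The film is dropped through Day 168 and kept from Day 169.

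**3. Number of subjects (assumed rate, constant over 168 days).** At 10%, 630 × 0.10 = 63 discontinue.
- Leaving in Days 141 to 168: 63 × 28/168 = 10.5, about 11 subjects (1.7%), or 10.5/6 = 1.75 per arm.
- Leaving in Days 162 to 168: 63 × 7/168 = 2.6, about 3 subjects.

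The counts are proportional to the rate. At 5% they are 31.5 × 28/168 = 5.3 and 31.5 × 7/168 = 1.3. At 20% they are 126 × 28/168 = 21 and 126 × 7/168 = 5.3. These are leavers, not lost films: someone leaving on Days 155 to 168 can be filmed on Day 169 or later (155 + 14 = 169).

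**4. Outer bound with a reused film.** Take the first film on the first consent date and the last on the last completion date.
- 1 April 2017 to 31 March 2018: 364 days, so the film is 364 - 168 = 196 days old at Day 1.
- 30 April 2017 to 1 March 2018: 305 days, so the film is 305 - 168 = 137 days old.

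**5. Effect of reuse on the arm contrast (all inputs assumed).** Share re-screened *q* = 2% to 20%, age of a reused film uniform over 22 to 196 days, common linear narrowing *r* = 0.1 to 0.3 mm per year, SD of change 0.4 to 0.8 mm.
- Largest extra pre-injection change in one subject: *r* × (196 - 22)/365.25 = 0.05 to 0.14 mm.
- Variance ratio: 1 + *r*² × (*v* - *v*₁)/SD². Here *v*₁ is the variance of film age, in years squared, with all films 10 to 22 days old, and *v* is that variance with share *q* reused. The largest value (*q* = 20%, *r* = 0.3, SD = 0.4) is 1 + 0.09 × 0.0141/0.16 = 1.008. The smallest (*q* = 2%, *r* = 0.1, SD = 0.8) is 1.00003.
- Expected bias in active minus vehicle: none, because film age is fixed before randomization.

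The variance ratio leaves out differences between subjects in narrowing rate, which would add to it.

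**The case against.** The best defence is that timing is well controlled where it matters. Every subject who does not reuse a film has an interval of 178 to 197 days. Reuse needs a re-screen, which is allowed once and only for a transient reason. The longest intervals need a subject filmed at the very start and injected at the very end of recruitment. Protocol 4.1 is an explicit exception to 7.3.1, not a contradiction of it, and the Image Review Charter, which is not available here, may govern which films are acceptable. The ET rule keeps the analysed intervals tight, and fewer than two leavers per arm fall in the last four weeks under the 10% assumption. All of this stands, and it limits the size of the point.

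A reader might infer more, and the documents do not support it:
- *The film interval is uncontrolled.* This is true only of re-screened subjects with a reused film.
- *The Week 24 structural endpoint is mistimed.* A dropped ET film is a missing value, not a mistimed one. With a reused film, follow-up after injection is still 24 weeks.
- *Old films dilute or bias the treatment contrast.* Pre-injection change is expected equally in all arms and cancels in the difference.
- *ET films practically never count.* The 14-day allowance lets some fall in Days 169 to 176.
- *A scheduled Week 24 film taken a day early is discarded.* SAP 9.2 concerns ET assessments only, and no such rule appears in the SAP.

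The defence does not explain why a subject's pain and function can count at Week 24 when a film from the same days cannot. Nor does it supply a missing-data sensitivity analysis for mJSW.

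**Conclusion.** The point holds as two separate, small defects. First, the one-sided ET window removes usable near-Week-24 films from a primary endpoint that has no second chance at measurement and no sensitivity analysis for missing values. Second, nothing in the protocol or SAP limits the age of a reused baseline film. This can lengthen the interval for an unknown number of re-screened subjects, at the cost of slight extra noise (under 1% of variance on the assumptions shown).

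The ET count rests on an assumed constant discontinuation rate and treats the day of leaving as the day of the film. The outer bound for reused films rests on estimated study dates. Neither defect threatens the trial's conclusions. Each concerns which data enter a primary analysis, and is better settled before unblinding than afterwards.

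**What to change.** Make both changes in the SAP. It describes randomization as already done (SAP 3.1), but Protocol 10.1 allows it to be finalized until database lock.

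1. **SAP 9.2.** For mJSW, assign an ET film to Week 24 if it was taken within 7 days either side of Day 169 (Days 162 to 176). For films from the normal screening window the interval is then 161 + 10 = 171 to 175 + 22 = 197 days. A wider window, such as from Day 141, admits intervals down to 140 + 10 = 150 days. It suits a sensitivity analysis, not the main one.
2. **SAP 9.4.** Add an mJSW sensitivity analysis that excludes subjects whose baseline film is more than 22 days before Day 1, and report how many there are. Film age is fixed before randomization, so this is not selection on a post-treatment event.

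The cost is about two sentences, a few ET films up to a week early, and one extra mJSW analysis. No additional radiograph is needed. Removing re-screened subjects from the main mJSW analysis is not worthwhile, since it would discard data to avoid very little noise.

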4.2 STUDY ENDPOINTS

4.2.1 PRIMARY ENDPOINTS

1. Evaluate change from baseline OA pain in the target knee as assessed by the weekly averages of daily pain Numeric Rating Scale (NRS) at Week 24
2. Evaluate change from baseline OA pain in the target knee as assessed by Western Ontario and McMaster Universities Osteoarthritis Index (WOMAC) pain subscore at Week 24
3. Evaluate change from baseline OA function in the target knee as assessed by WOMAC physical function subscore at Week 24
4. Evaluate change from baseline in medial joint space width (JSW) as documented by radiograph of the target knee at Week 24

4.2.2 SECONDARY ENDPOINTS

1. Evaluate the safety of SM04690 as measured by treatment-emergent adverse events (TEAEs)
2. Evaluate change from baseline OA disease activity as assessed by Patient Global Assessment at Week 24

4.2.3 EXPLORATORY ENDPOINTS

1. Evaluate change from baseline OA pain in the target knee as assessed by WOMAC pain subscore at Week 4, 8, 12, 16, and 20
2. Evaluate change from baseline OA function in the target knee as assessed by WOMAC physical function subscore at Week 4, 8, 12, 16, and 20
3. Evaluate change from baseline symptoms of OA in the target knee as assessed by WOMAC total score at Week 4, 8, 12, 16, 20, and 24
4. Evaluate change from baseline OA pain in the target knee at each week (aside from Week 24) as assessed by weekly averages of daily pain NRS
5. Evaluate change from baseline OA disease activity as assessed by Patient Global Assessment at Week 4, 8, 12, 16, and 20
6. Evaluate change from baseline OA function in the target knee as assessed by Knee Injury and Osteoarthritis Outcome Score (KOOS) at Week 4, 8, 12, 16, 20, and 24
7. Evaluate change from baseline OA function in the target knee at each week as assessed by KOOS Physical Function Short Form (KOOS-PS)
8. Evaluate change from baseline OA disease activity as assessed by Physician Global Assessment at Week 4, 12, and 24
9. Evaluate change over time in NSAID usage as assessed by weekly averages of daily pain medication electronic diary responses at every week
10. Evaluate subject perception of study treatment received at Week 24
11. Evaluate outcome differences between treatment with sham or placebo injections at Week 4, 8, 12, 16, 20, and 24

